4.2.2 Axitinib dose reduction and re-escalation

Dosing interruption and/or dose reduction by 1, and if needed, 2 dose levels (one dose level decrease at a time) as indicated in Table 1 will be allowed depending on the type and severity of toxicity encountered. Patients who have undergone dose reduction may undergo dose re-escalation to prior dose levels in the absence of grade 2 or greater AEs for at least 28 days.

If patient develops decompensated cirrhosis (Child Pugh B), axitinib dosing should be reduced to the -1 dose level. Subsequent dosing can be increased or decreased according to the patient's tolerance. Patients must not have irreversible toxicities related to the axitinib to be eligible for dose re-escalation of axitinib after dose reduction.

Table 1. Axitinib dose levels.

Dose level	Dose
0	5 mg BID
-1	3 mg BID
-2	2 mg BID

Further dose reductions less than dose level -2 are not permitted.

4.2.3 Axitinib dose modifications, and avelumab and bavituximab infusion omissions for treatment-related toxicities.

Toxicities related to axitinib may primarily stem from the known on-target effects of inhibiting VEGFR including hypertension and proteinuria. In contrast, toxicities related to avelumab and bavituximab may be due to immune related AEs (irAEs). Management of specific irAEs should be consistent with American Society of Clinical Oncology (ASCO) Clinical Practice Guidelines (2018). For Grade 2 irAEs, avelumab and bavituximab should be permanently discontinued if AE does not resolve to at least Grade 1 within 12 weeks of last dose or corticosteroids cannot be reduced to ≤ 10 mg prednisone or equivalent per day within 12 weeks. Specific dose modifications and infusion omissions depend on the severity of toxicities as detailed in Table 2 and Table 3.

If any study drug is withheld or discontinued, the remaining study drugs can be continued as long as the patient is experiencing clinical benefit, as determined by the investigator per medical judgment.

Table 2. Dose modifications and infusion omissions for toxicities.

Toxicity	NCI CTCAE Grade	Axitinib	Avelumab	Bavituximab
Hypertension	1	Continue at same dose level.	Continue as per schedule.	Continue as per schedule.
	2	If not on maximal anti-hypertensive treatment, institute new or additional antihypertensive medication and continue at the same dose level. If on maximal anti-hypertensive treatment, reduce by 1 dose level.	Continue as per schedule.	Continue as per schedule.
	3	For first and subsequent occurrence, withhold until BP is less than 150/100 mm Hg and adjust antihypertensive medication. Then, reduce by 1 dose level and resume treatment.	Continue as per schedule.	Continue as per schedule.

		
If on maximal anti-hypertensive treatment, reduce by 1 dose level.
 
If axitinib dosing is interrupted, patients receiving antihypertensive medications should be monitored closely for hypotension as BP usually decreases within 1-2 days after the last dose.
		
	4	
Repeat dose reduction by one lower dose level.
 
Permanent discontinuation if already on maximal anti-hypertensive treatment.
	Continue as per schedule.	Continue as per schedule.
Proteinuria	1	Continue at same dose level.	Continue as per schedule.	Continue as per schedule.
	2-3	
Continue at same dose level if proteinuria is <2gm/24 hours.
 
If proteinuria is >2gm/24 hours, withhold until proteinuria is <2 g/24 hours.
 
Time of repeat urine collection is at investigator discretion.
 
Then, resume at the same dose level or reduce by 1 dose level as per investigator judgment.
	Continue as per schedule.	Continue as per schedule.
irAEs (except for endocrinopathies)	1	Continue at same dose level.	Continue as per schedule.	Continue as per schedule.
	2	Continue at same dose level.	Withhold until Grade ≤1. If Grade 2 event does not resolve to Grade 1 after holding for at least 2 cycles (8 weeks), permanently discontinue.	Withhold until Grade ≤1. If Grade 2 event does not resolve to Grade 1 after holding for at least 2 cycles (8 weeks), permanently discontinue.
	3-4	Hold treatment until Grade ≤1 and restart at same dose level.	Permanently discontinue.	Permanently discontinue.
Immune related hypothyroidism	1	Continue at same dose level.	Continue as per schedule.	Continue as per schedule.
	2	Continue at same dose level.	May hold until patient is on thyroid hormone supplementation or symptoms resolve to baseline.	May hold until patient is on thyroid hormone supplementation or symptoms resolve to baseline.

	3-4	Hold treatment until Grade ≤ 1 and restart at same dose level.	Hold until symptoms resolve to baseline or until Grade ≤ 1 while on thyroid supplementation. Patient should be referred to Endocrine.	Hold until symptoms resolve to baseline or until Grade ≤ 1 while on thyroid supplementation. Patient should be referred to Endocrine.
Immune related hyperthyroidism	1	Continue at same dose level.	Continue as per schedule.	Continue as per schedule.
	2	Continue at same dose level.	May hold until patient symptoms resolve to baseline. Consider β - blockers for symptomatic control rather than steroids initially. For persistent symptoms >6 weeks, patient will need to be evaluated for Grave's disease.	May hold until patient symptoms resolve to baseline. Consider β - blockers for symptomatic control rather than steroids initially. For persistent symptoms >6 weeks, patient will need to be evaluated for Grave's disease.
	3-4	Hold treatment until Grade ≤ 1 and restart at same dose level.	Hold until symptoms resolve to baseline or until Grade ≤ 1 with appropriate therapy. Patient should be referred to Endocrine.	Hold until symptoms resolve to baseline or until Grade ≤ 1 with appropriate therapy. Patient should be referred to Endocrine.
Immune related adrenal insufficiency	1	Continue at same dose level.	Continue as per schedule.	Continue as per schedule.
	2	Continue at same dose level.	Hold until symptoms resolve to baseline or until Grade ≤ 1 with replacement hormones. Maintenance replacement therapy with prednisone 5-10 mg daily (or equivalent). May require fludrocortisone (0.1 mg/d) for mineralcorticoid replacement. May need to use doses 2-3 times maintenance dose for management of acute symptoms.	Hold until symptoms resolve to baseline or until Grade ≤ 1 with replacement hormones. Maintenance replacement therapy with prednisone 5-10 mg daily (or equivalent). May require fludrocortisone (0.1 mg/d) for mineralcorticoid replacement. May need to use doses 2-3 times maintenance dose for management of acute symptoms.
	3-4	Permanently discontinue.	Permanently discontinue.	Permanently discontinue.
Immune related hypophysitis	1	Continue at same dose level.	Consider holding until patient is stabilized on replacement therapy. Patient should be referred to Endocrine.	Consider holding until patient is stabilized on replacement therapy. Patient should be referred to Endocrine.
	2	Continue at same dose level.	Hold until symptoms resolve to baseline or until Grade ≤ 1 with replacement hormones. Patient should be referred to Endocrine.	Hold until symptoms resolve to baseline or until Grade ≤ 1 with replacement hormones. Patient should be referred to Endocrine.

	3-4	Permanently discontinue.	Permanently discontinue.	Permanently discontinue.
Immune related diabetes	1	Continue at same dose level.	Continue as per schedule.	Continue as per schedule.
	2	Continue at same dose level.	Considering holding until patient is stabilized (Grade ≤ 1) on replacement therapy. Insulin should be initiated as default treatment rather than oral therapies. Patient should be referred to Endocrine.	Considering holding until patient is stabilized (Grade ≤ 1) on replacement therapy. Insulin should be initiated as default treatment rather than oral therapies. Patient should be referred to Endocrine.
	3-4	Hold treatment until Grade ≤ 1 and restart at same dose level.	Hold until patient is stabilized (Grade ≤ 1) on replacement therapy. Insulin should be initiated as default treatment rather than oral therapies. Patient should be referred to Endocrine.	Hold until patient is stabilized (Grade ≤ 1) on replacement therapy. Insulin should be initiated as default treatment rather than oral therapies. Patient should be referred to Endocrine.
Immune related colitis/diarrhea	1	Continue at same dose level.	Consider holding until symptoms resolve to baseline or until Grade ≤ 1 . Consider antidiarrheals if other causes are excluded.	Consider holding until symptoms resolve to baseline or until Grade ≤ 1 . Consider antidiarrheals if other causes are excluded.
	2	Continue at same dose level.	Hold until symptoms resolve to baseline or until Grade ≤ 1 . Steroids may be considered if indicated on an individual basis.	Hold until symptoms resolve to baseline or until Grade ≤ 1 . Steroids may be considered if indicated on an individual basis.
	3	Hold treatment until Grade ≤ 1 and restart at same dose level.	Hold until symptoms resolve to baseline or until Grade ≤ 1 . Administer steroids at 1-2 mg/kg/d prednisone or equivalent with taper over 4 weeks. Patient should be referred to Gastroenterology. Consider colonoscopy.	Hold until symptoms resolve to baseline or until Grade ≤ 1 . Administer steroids at 1-2 mg/kg/d prednisone or equivalent with taper over 4 weeks. Patient should be referred to Gastroenterology. Consider colonoscopy.
	4	Permanently discontinue.	Permanently discontinue.	Permanently discontinue.
Immune related pneumonitis	1	Continue at same dose level.	Hold if there is progression with repeat CT chest at 3-4 weeks and treat as Grade 2.	Hold if there is progression with repeat CT chest at 3-4 weeks and treat as Grade 2.
	2	Continue at same dose level.	Hold until symptoms resolve to baseline or until Grade ≤ 1 . Administer steroids at 1-	Hold until symptoms resolve to baseline or until Grade ≤ 1 . Administer steroids at 1-

			2 mg/kg/d prednisone or equivalent with taper over 4 weeks. Consider Pulmonology consult. Monitor every 3-4 days, if no clinical improvement, treat as Grade 3.	2 mg/kg/d prednisone or equivalent with taper over 4 weeks. Consider Pulmonology consult. Monitor every 3-4 days, if no clinical improvement, treat as Grade 3.
	3-4	Permanently discontinue.	Permanently discontinue.	Permanently discontinue.
Immune related hepatitis	1	Continue at same dose level.	Continue as per schedule.	Continue as per schedule.
	2	Continue at same dose level.	Hold until symptoms resolve to baseline or until Grade ≤ 1 . Steroids may be considered if indicated on an individual basis.	Hold until symptoms resolve to baseline or until Grade ≤ 1 . Steroids may be considered if indicated on an individual basis.
	3-4	Permanently discontinue.	Permanently discontinue.	Permanently discontinue.

Table 3. Dose modifications for drug-related adverse events potentially associated with axitinib and not considered immune-related.

Toxicity	NCI CTCAE Grade	Axitinib
Diarrhea	1-2	Continue at same dose level.
	3	Hold until symptoms resolve to baseline or until Grade ≤ 1 . Then, resume at the same dose level or reduce by 1 dose level as per investigator judgment.
	4	Permanently discontinue.
Hemorrhage/bleeding	1	For CNS bleeding, permanently discontinue. For non-CNS bleeding, continue at same dose level.
	2	For pulmonary and GI bleed (other than hemorrhoidal bleeding or in setting of colitis), permanently discontinue. For other bleeding events, hold until symptoms resolve to baseline or until Grade ≤ 1 . Then, resume at the same dose level or reduce by 1 dose level as per investigator judgment.
	3-4	Permanently discontinue.
Palmar-plantar erythrodysesthesia syndrome	1-2	Continue at same dose level. Consider the use of topical pain relievers and/or moisturizing exfoliant creams.
	3	Hold until symptoms resolve to baseline or until Grade ≤ 1 . Consider the use of topical or parenteral pain relievers and/or moisturizing exfoliant creams. Then, resume at the same dose level or reduce by 1 dose level as per investigator judgment.
AST, ALT or bilirubin elevation	1	Continue at same dose level.
	2	Hold until symptoms resolve to baseline or until Grade ≤ 1 . Then, resume at same dose level.
	3-4	Hold until symptoms resolve to baseline or until Grade ≤ 1 . Then, reduce by 1 dose level.
Hematologic abnormalities	1-3	Continue at same dose level.

	4	Hold until symptoms resolve to baseline or until Grade ≤1. Restart axitinib dose reduced by 1 dose level. Note: Grade 4 lymphopenia not associated with clinical events, (e.g, opportunistic infection) may continue on with axitinib.
Stevens-Johnson syndrome	3-4	Permanently discontinue.
Other non-hematologic toxicities and laboratory abnormalities	1-2	Continue at same dose level.
	3	Hold until symptoms resolve to baseline or until Grade ≤2. For toxicities controlled with symptomatic medications or asymptomatic laboratory abnormalities, continue at the same dose level or reduce by 1 dose level as per investigator judgment. For all other toxicities, reduce by 1 dose level.
	4	Hold until symptoms resolve to baseline or until Grade ≤2. Then, reduce by 1 dose level as per investigator judgment. Permanently discontinue axitinib for Grade 4 toxicities that meet any of the following conditions: 1) recurrent 2) life-threatening 3) reversible posterior leukoencephalopathy syndrome 4) arterial thrombosis/ischemia

4.2.4 Infusion related reactions.

Because avelumab and bavituximab are administered as infusions, infusion reactions are possible and may include symptoms such as fever, chills, shortness of breath, headache, and rigors. Infusion modifications depend on the severity of reactions as detailed in Table 4 below.

Table 4. Infusion-related reactions caused by avelumab or bavituximab.

NCI CTCAE Grade	Infusion modifications
1	Decrease the avelumab and/or bavituximab infusion rate by 50%.
2	Temporarily discontinue avelumab and/or bavituximab infusion. Resume infusion at 50% of previous rate once infusion-related reaction has resolved or decreased to at least Grade 1 in severity, and monitor closely for any worsening.
3-4	Stop the infusion immediately and disconnect infusion tubing from the patient. Patients may not receive further treatment.

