4.5 Duration of Therapy

Study treatment with axitinib, avelumab, and bavituximab will continue until disease progression, unacceptable toxicity, death, or discontinuation from the study treatment for any other reason.

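### For patients not on maximal antihypertensives, the Table 2 cell for Grade 4 hypertension omits the axitinib hold that Grade 3 requires and section 7.1.2 calls for

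*Combined protocol and SAP*

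**What the plan says.** Section 4.2.3 makes the tables the working rule for dose changes: "Specific dose modifications and infusion omissions depend on the severity of toxicities as detailed in Table 2 and Table 3".

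For hypertension, the axitinib column of Table 2 reads as follows.

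- **Grade 3:** "For first and subsequent occurrence, withhold until BP is less than 150/100 mm Hg and adjust antihypertensive medication". Treatment then restarts one level lower. A further line gives a one-level reduction for patients on maximal antihypertensives.
- **Grade 4:** "Repeat dose reduction by one lower dose level". A second line adds "Permanent discontinuation if already on maximal anti-hypertensive treatment".

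Three other places bear on the point.

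- Section 4.2.2 allows dosing to be interrupted or reduced, one level at a time, and sets a floor: "Further dose reductions less than dose level -2 are not permitted".
- Section 7.1.2 (Hypertension) says that in severe hypertension axitinib is to be held, then restarted at a lower level after improvement.
- Section 7.4.1 defines Grade 3 as severe and Grade 4 as life-threatening.

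**The concern.** A dose-modification table should not become less protective as the grade rises. Here, for a patient not on maximal antihypertensives, moving from Grade 3 to Grade 4 removes three written instructions: the hold, the blood-pressure threshold for restarting, and the antihypertensive adjustment. Only the one-level reduction remains.

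Patient safety is what is at stake. A site that does what the cell states, and no more, would lower the dose during a life-threatening event where it would have stopped the drug for a lesser one. Hypertension is also the toxicity for which this row most needs to be clear: section 1.2.3 reports it as the most common Grade 3 treatment-related event with avelumab plus axitinib in HCC (50.0% of 22 patients).

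**Working it through.** The plan gives no figure on this point to reproduce. The check is a comparison of texts, followed by a rough estimate of how often the cell would be used.

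**1. Grade 3 against Grade 4, patient not on maximal antihypertensives (Table 2, axitinib column)**

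| Element | Grade 3 | Grade 4 |
|---|---|---|
| Hold | Yes, at every occurrence | Not stated |
| Restart threshold | Below 150/100 mm Hg | Not stated |
| Adjust antihypertensives | Yes | Not stated |
| Reduce one level | Yes, after the hold | Yes |

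For a patient on maximal antihypertensives, Grade 4 means permanent discontinuation. That rule is clear, is stricter than Grade 3, and is not criticised.

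**2. Against section 7.1.2.** The hold there applies to severe hypertension. Grade 3 is severe and Grade 4 is worse, so the hold applies at least as strongly to Grade 4.

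**3. Against the other Grade 4 cells for axitinib**

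- Table 2 has 10: hypertension, general irAEs, hypothyroidism, hyperthyroidism, adrenal insufficiency, hypophysitis, diabetes, colitis, pneumonitis, hepatitis.
- Table 3 has 6: diarrhea, hemorrhage, AST/ALT/bilirubin, hematologic, Stevens-Johnson syndrome, other non-hematologic.
- Starting with a hold or permanent discontinuation: 9 + 6 = 15 of 16. The exception is hypertension. (The hematologic cell exempts lymphopenia without clinical events.)

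**4. How often the cell would be used.** Inputs: a 1% Grade 4 hypertension rate from pooled RCC studies (section 7.1.2), assumed to carry over to this trial; 14 patients in stage 1 and 29 evaluable at most (section 10.2). The chance of at least one case is 1 − (1 − p)^n.

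| Assumed rate p | n = 14 | n = 29 |
|---|---|---|
| 0.5% | 6.8% | 13.5% |
| 1% | 13.1% | 25.3% |
| 2% | 24.6% | 44.3% |

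These rows count all patients. The documents do not give the share of cases arising in patients not on maximal antihypertensives. With assumed shares, at the 1% rate and n = 29:

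- share 50%: p = 0.5%, and 1 − 0.995^29 = 13.5%
- share 25%: p = 0.25%, and 1 − 0.9975^29 = 7.0%

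Patients replaced under section 10.2 would add to the number treated, so 29 slightly understates exposure.

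**The case against.** The strongest reply is that the cell is incomplete, not contradictory. It is silent on holding and does not tell the site to keep dosing. Holding until blood pressure improves and then restarting one level lower satisfies the cell, section 4.2.2 and section 7.1.2 together. Section 5.4 lets the investigator stop for unsafe toxicity, and section 4.5 lists unacceptable toxicity as a reason to end treatment. All of this stands. A reader might infer that the protocol forbids a hold at Grade 4, or that a site must set the cell aside to give one; the documents support neither. What remains is that these sections permit or advise a hold, while the table that governs dosing does not require it.

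It can also be argued that *repeat* refers back to the whole Grade 3 sequence. That is possible, but the cell names only the dose reduction. A patient whose first event is Grade 4 has no earlier step to repeat, and the Grade 3 cell already covers later Grade 3 occurrences.

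A third reply concerns dose level -2, where the cell's only action is barred by section 4.2.2. A reader might take this as a defect peculiar to Grade 4 hypertension. It is not: the same gap exists wherever a one-level reduction is ordered, including Grade 3 hypertension and the AST/ALT/bilirubin, hematologic and other non-hematologic rows of Table 3.

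Finally, a reader might infer that Grade 4 events must end axitinib, since the Table 3 row for other non-hematologic toxicities says "Permanently discontinue axitinib for Grade 4 toxicities that meet any of the following conditions: 1) recurrent 2) life-threatening". Hypertension has its own row in Table 2, and outright discontinuation would depart from the restart at a lower level in section 7.1.2. That choice is a clinical preference, which the documents do not settle.

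**Conclusion.** The point holds as a safety omission in one table cell. For patients not on maximal antihypertensives, the Grade 4 hypertension instruction for axitinib is less protective as written than the Grade 3 instruction and lacks the hold in section 7.1.2. It should be fixed, although nothing in the protocol prevents a site from holding the drug.

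The expected frequency is low: about 25% for at least one Grade 4 case in 29 patients, and about 7% to 14% in the affected group. These figures rest on the RCC rate of 1% carrying over and on assumed shares of 25% to 50%.

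A larger figure is tempting. Grade 3 hypertension was 50.0% in the HCC avelumab-axitinib study against 22% in RCC; scaling Grade 4 alike gives 1% × 50/22 = 2.27%, and 49% in 29 patients. The documents do not support that step. The HCC study saw no Grade 4 or 5 toxicity in 22 patients (two-sided 95% upper limit 1 − 0.025^(1/22) = 15.4%, which is too wide to settle the rate). The 49% also counts all patients, not only the affected group.

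The primary endpoint, the decision rule and the sample size are unaffected.

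**What to change.** Rewrite the Grade 4 hypertension cell for axitinib so that it says three things:

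1. Hold axitinib until blood pressure falls below 150/100 mm Hg, and adjust the antihypertensive regimen.
2. Restart one dose level lower.
3. Stop axitinib permanently if the patient was already on maximal antihypertensives or was already at dose level -2.

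This uses the protocol's own Grade 3 steps, agrees with section 7.1.2 and keeps the existing discontinuation rule. Because the level -2 gap is shared with other cells, add one sentence to section 4.2.2 stating what happens when a reduction is called for and the patient is already at the lowest level.

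The cost is one table cell and one sentence in the next amendment, with no added visits, tests or patients. The downside is slightly less axitinib exposure in a rare event.

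### Table 2's general immune-related row also covers colitis, pneumonitis and hepatitis, and conflicts with their own rows on four grade 3-4 lines, with no rule on which governs

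*Combined protocol and SAP*

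**What the plan says.** Section 4.2.3 sends sites to Table 2 and Table 3 for dose changes according to severity. In Table 2 the general row for immune-related events is labelled "irAEs (except for endocrinopathies". At grade 3-4 it permanently discontinues avelumab and bavituximab, and for axitinib it says "Hold treatment until Grade ≤1 and restart at same dose level".

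Five endocrine rows follow (hypothyroidism, hyperthyroidism, adrenal insufficiency, hypophysitis, diabetes), and the label exempts these. Three further rows then cover events that the label does not exempt:

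- Colitis/diarrhea. At grade 3 the antibody cells begin "Hold until symptoms resolve to baseline or until Grade" 1 or lower, and add "Administer steroids at 1-2 mg/kg/d prednisone or equivalent with taper over 4 weeks. Patient should be referred to Gastroenterology". At grade 4 all three drugs are permanently discontinued.
- "Immune related pneumonitis". At grade 3-4 all three drugs are permanently discontinued.
- "Immune related hepatitis". At grade 3-4 all three drugs are permanently discontinued.

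The 4.2.3 text also sets a limit for grade 2 immune-related events. The antibodies stop for good if the event has not resolved to grade 1 within 12 weeks of the last dose, or if steroids cannot be brought down to 10 mg of prednisone per day or less within 12 weeks. The limit names grade 2 only.

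**The concern.** A site facing grade 3-4 immune colitis, pneumonitis or hepatitis finds two rows in the same table that both describe its patient. On four lines it cannot comply with both.

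At grade 3 colitis, one row forbids giving the antibodies again and the other allows it after recovery. On the other three lines the antibodies stop either way, so the axitinib cell decides the outcome: the patient either leaves all study treatment or can return to axitinib at the same dose. Section 4.2.3 lets remaining drugs continue while the investigator sees clinical benefit, so the second outcome is a real option.

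Section 11.5 requires strict adherence to the approved protocol outside emergencies. Whichever row a site follows, the other can be cited against it as a deviation.

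**Working it through.** The plan states no figure on this point to reproduce. The check is a cell-by-cell comparison within Table 2.

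| Line | Drug | General row | Event-specific row | Same? |
|---|---|---|---|---|
| Colitis, grade 3 | Axitinib | Hold, resume same dose | Hold, resume same dose | Yes |
| | Avelumab | Stop for good | Hold until recovery | **No** |
| | Bavituximab | Stop for good | Hold until recovery | **No** |
| Colitis, grade 4 | Axitinib | Hold, resume same dose | Stop for good | **No** |
| | Both antibodies | Stop for good | Stop for good | Yes |
| Pneumonitis, grade 3-4 | Axitinib | Hold, resume same dose | Stop for good | **No** |
| | Both antibodies | Stop for good | Stop for good | Yes |
| Hepatitis, grade 3-4 | Axitinib | Hold, resume same dose | Stop for good | **No** |
| | Both antibodies | Stop for good | Stop for good | Yes |

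Four lines times three drugs gives 12 cells. They differ in 2 + 1 + 1 + 1 = 5 and agree in 7. Every one of the four lines has at least one conflict.

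Neither row is the safer one throughout. The general row is stricter on the antibodies at grade 3 colitis and looser on axitinib on the other three lines. Taking the more cautious row would therefore mean mixing the two.

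**Is there a precedence rule?** The 4.2.3 text points to the tables without ranking rows. Section 7.2.2 says that avelumab may be delayed or stopped depending on severity, which leaves both options open. No rule appears elsewhere in section 4.2 or in section 5.4.

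**Which row is probably meant?** Table 3 gives a clue. For non-immune events it permanently stops axitinib at grade 4 diarrhea, and it requires a one-level reduction after grade 3-4 AST, ALT or bilirubin elevation. Under the general row, the immune-related counterparts would return to the same axitinib dose, which is more lenient than the non-immune rule. That favours the specific rows.

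**How often?** Section 1.2.9 reports grade 3-4 colitis/diarrhea in 2 of 36 HCC patients on pembrolizumab plus bavituximab.

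- 2/36 = 5.6%, Clopper-Pearson 95% CI 0.7% to 18.7%.
- Applied to 29 evaluable patients: 0.056 x 29 = 1.6, with limits 0.2 and 5.4.

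This is context only. It combines colitis with diarrhea and grade 3 with grade 4, comes from a preliminary analysis, and involves a different checkpoint antibody and no axitinib.

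**The case against.** The best reply is that this is a labelling slip with one sensible reading. The three event rows carry their own steroid doses, referrals and work-up, and their grade 3-4 lines would serve no purpose if the general row governed. On that reading every conflict disappears. The argument about intent stands. It does not dispose of the point, because the authors saw that the general row could overlap others and exempted only the endocrine group, and no sentence states the convention.

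A second reply is that 4.2.3 defers to an outside guideline for managing specific immune-related events. The guideline is not reproduced, so its content cannot be checked here. The protocol does not present it as a way of choosing between rows of Table 2.

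A third is that harm is contained. Resumption requires recovery, the physician may remove a patient (5.4), and toxicity is reviewed in real time by the GI DOT and DSMC (11.4). All true, but none of these tells a site which row to follow.

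Some stronger readings are tempting and fail:

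- A reader might infer that grade 2 colitis, pneumonitis and hepatitis holds have no time limit, because their rows give none. The 12-week and steroid limit in the 4.2.3 text applies to all grade 2 immune-related events.
- A reader might infer that the grade 3 colitis row lacks any taper. It instructs one over 4 weeks. What it lacks is a maximum hold and a rule for a failed taper.
- A reader might add that the grade 4 hypertension cell omits a hold. Section 7.1.2 supplies it.
- A reader might size the problem from the diarrhea rates reported for axitinib alone or with avelumab. Those events need not be immune-related, and non-immune diarrhea has its own row in Table 3.

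**Conclusion.** The concern holds as a conflict between stated dosing rules, not as missing detail. Four grade 3-4 lines in Table 2 carry two instructions that cannot both be followed, and the protocol does not rank them. The antibodies are affected only at grade 3 colitis. Axitinib is affected at grade 4 colitis, grade 3-4 pneumonitis and grade 3-4 hepatitis.

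Few patients are likely to be affected. The nearest rate suggests one or two of 29 with grade 3-4 colitis/diarrhea, with wide uncertainty and on the assumption that a different regimen is a fair guide. The specific rows are probably intended, but that is inference.

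A reader might go further and infer damage to the primary analysis. The documents do not support that: the two-stage design, its error rates and the definition of objective response do not depend on which row is used. The case for change rests on patient safety and consistent dosing alone. The change should be made, because the events are serious and the correction is small.

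**What to change.** 1. Relabel the general row *irAEs other than those with their own row below*, and add a note to Table 2 that the event-specific row governs.
2. Have the sponsor's clinicians confirm that the grade 3 colitis hold of the antibodies, and the permanent axitinib stops at grade 4 colitis and grade 3-4 pneumonitis and hepatitis, are what they intend.
3. If the grade 3 colitis hold is kept, extend to it the limit that 4.2.3 already sets for grade 2 events: recovery within 12 weeks of the last dose, and steroids down to 10 mg of prednisone per day or less within 12 weeks.

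The cost is a wording amendment of one row label, one table note and one extended sentence. Sample size, procedures and error rates stay as they are.
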